4.1. Primary outcome

- percentage (%) of complete root coverage (CRC) at 12 months

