4.2. Secondary outcomes

- percentage of root coverage (RC %) at 3, 6 and 12 months
- keratinized tissue width (KTW) at 3, 6 and 12 months
- gingival thickness (GT) at 3, 6 and 12 months
- post-surgical pain (PP),
- amount of drug intake after surgery
- patient perception of aesthetics at 6 and 12 months
- color match (blending), contour (correct outline of the gingival margin at adjacent teeth), contiguity (evaluated based on the visible confluence between the treated area and the adjacent soft tissues), degree of keloid formation scored at the 1-year post-surgical evaluation will be measured by an expert periodontist.
- duration of surgery (from anesthesia to last suture).

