5. STUDY DESIGN

5.1. Description of the protocol

The present research is a monocentric prospective parallel randomized controlled clinical trial.

Patients presenting multiple gingival recessions in the maxillae will be enrolled in the study after having signed an informed consent. Recessions will be treated by means of two mucogingival surgery techniques: modified coronally advanced flap (MCAF) and modified coronally advanced tunnel technique (MCAT), in association with the use of a collagen matrix (CM).

An allocation sequence by means of a computer-generated random list will be created and a sealed opaque envelope will contain the type of treatment assigned to each patient. The opaque envelope will be opened immediately after performing anesthesia.

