6.1. Inclusion criteria

Subjects must be males and females of at least 18 years of age with:

- multiple (i.e., at least 2) Miller Class I and/or II gingival recessions located in the maxillae, with an apico-coronal extension (i.e., defect depth > 1 mm with at least one defect > 2 mm) and with at least 1 mm of residual keratinized tissue,
- good general health, with no systemic diseases that could influence the outcome of the therapy,
- healthy periodontal conditions (i.e., no presence of sites ≥ 4 mm and/or presence of intra-bony defects in the selected sites),
- adequate oral hygiene (full mouth plaque score (FMPS) of <25% at baseline (following initial oral hygiene instructions and prophylaxis),
- an adequate control of inflammation (full mouth bleeding score [FMBS]) of <25% at baseline (following initial oral hygiene instructions and prophylaxis).

Subjects must have voluntarily signed the informed consent before any study related action and must be committed to the study and the required follow-up visits.

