The porcine-derived bio-resorbable collagen matrix (CM) (Fibro-Gide) is now prepared for placement on the interested areas: the width of the matrix must be reduced to 3-4 mm and the matrix has to adapt to the receiving tissues, when placed, a suture (6/00) must be used to hold it in position. Sling sutures (6/00) are performed to accomplish a precise adaptation of the buccal flap on the exposed root surfaces and to stabilize every single surgical papilla over the interdental connective tissue bed.

- Modified coronally advanced tunnel technique (MCAT)

Immediately before surgery, composite stops are placed at the contact points to prevent collapse of the future suspended sutures into the inter-proximal spaces.

After local anaesthesia, root planing of the exposed root surface is performed by means of hand instruments. Ethylenediaminetetraacetic (EDTA) is applied on the sites.

Subsequently, intra-sulcular incisions were placed and muco-periosteal flap separation are raised using sharp tunnel elevators. The muco-periosteal dissection is extended beyond the muco-gingival junction (MGJ) and under each papilla, to allow passive, tension-free mobilization in coronal direction. Muscle fibres and any remaining collagen bundles on the inner aspect of the flap alveolar mucosa are cut using Gracey curettes with extreme care in order to obtain a passive coronal positioning of the flap and the papilla and to avoid perforation of the flap.

The porcine-derived bio-resorbable collagen matrix (Fibro-Gide) is now prepared for placement on the interested areas: the width of the matrix must be reduced to 3-4 mm, then it can be inserted under the CAMT by starting at the deepest recession. Then, the site is rinsed with saline solution to remove any clot. The matrix has to be held in position using a suture (6/00).

Finally, the flap is positioned coronally to CEJ by means of suspended sutures (6/00) around the contact points.

At surgery, the duration of the full procedure will be evaluated (from anesthesia to suture).

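### The number of recessions treated is open-ended and drives surgery time, yet it is neither a stratification factor nor a covariate, which costs precision in the per-patient secondary outcomes

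*Combined protocol and SAP*

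**What the plan says.** Section 6.1 of the combined protocol and SAP admits patients with "multiple (i.e., at least 2) Miller Class I and/or II gingival recessions located in the maxillae". It sets a minimum and no maximum.

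Section 4.2 lists "duration of surgery (from anesthesia to last suture" and "amount of drug intake after surgery" as secondary outcomes, together with post-surgical pain. Section 7.2 confirms that the whole operation is timed: "At surgery, the duration of the full procedure will be evaluated (from anesthesia to suture". The flow chart and section 7.5 place a single pain assessment at day 7. All three outcomes therefore yield one value per patient.

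On allocation, section 5.1 says: "An allocation sequence by means of a computer-generated random list will be created and a sealed opaque envelope will contain the type of treatment assigned". Allocation is by patient, and no stratification factor is named. The same section adds: "The opaque envelope will be opened immediately after performing anesthesia". The flow chart has recession depth measured at screening, so the number of recessions is available before allocation.

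Section 8.3 plans t-tests for numerical data (its list includes the VAS but not duration or drug intake), Fisher's exact test for the frequency of complete root coverage (CRC), and permutation p-values. It also plans analyses at both patient and tooth level and a mixed model for patient and tooth factors. The number of treated teeth appears nowhere as a covariate, offset or stratum.

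**The concern.** The surgical steps in section 7.2 accumulate with each tooth. In the flap technique every papilla is dissected, de-epithelialised and sutured. In the tunnel technique the dissection passes under each papilla, and sutures are suspended at the contact points. Total operating time must therefore rise with the number of recessions treated. Pain and drug intake plausibly rise too, although the documents give no data on that.

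The difference of interest is between techniques. If a patient with two recessions and a patient with six are compared without regard to extent, variation in extent becomes noise in the comparison. With 18 patients per arm, it can also fall unevenly by chance. Discomfort is part of the secondary objective in section 4, so these outcomes matter to the trial.

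The mixed model does not solve this. A tooth-level random effect needs tooth-level observations, and duration, pain and drug intake have none. Only a patient-level covariate or strata would remove the effect of extent, and neither is specified.

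**Working it through.** **The plan's own figure.** Section 8.1 gives 17 per arm for a 10-point difference in mean root coverage with SD 10, alpha 0.05 and power 80%. A two-sided two-sample t-test needs 16.71, rounded up to 17, with power 80.7% at 17. The figure reproduces. It concerns mean root coverage, so it does not bear on this point either way.

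**Inputs.** From the documents: 18 per arm and at least 2 recessions per patient. Assumed, because the documents are silent: 2-4 or 2-6 teeth with equal probability, b = 5 or 10 minutes per tooth, residual SD s = 10 or 20 minutes, and a true technique difference of 15 minutes for the power figures.

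**Chance imbalance.** The variance V of the tooth count is 2/3 for 2-4 teeth and 2 for 2-6 teeth. The SD of the difference in arm means is √(2V/18):
- 2-4 teeth: √(2 × 0.667/18) = 0.27
- 2-6 teeth: √(2 × 2/18) = 0.47

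From the exact distribution, the arm means differ by more than half a tooth in 5.2% and 26.4% of trials. At 5-10 minutes per tooth, half a tooth shifts the raw difference in duration by 2.5 to 5 minutes.

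**Share of duration variance explained.** Share = b²V/(b²V + s²). The raw standard error is √[(b²V + s²) × 2/18]. After adjustment it is close to s√(2/18), which is 3.3 minutes for s = 10 and 6.7 for s = 20. Raw power is from the t-test; adjusted power is from simulation of 40,000 trials per setting.

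| Teeth | b | s | Share | Raw SE (min) | Power, raw | Power, adjusted |
|---|---|---|---|---|---|---|
| 2-4 | 5 | 20 | 4% | 6.8 | 57% | about 58% |
| 2-4 | 5 | 10 | 14% | 3.6 | 98% | 99% |
| 2-4 | 10 | 20 | 14% | 7.2 | 53% | about 58% |
| 2-4 | 10 | 10 | 40% | 4.3 | 92% | 99% |
| 2-6 | 5 | 20 | 11% | 7.1 | 54% | about 58% |
| 2-6 | 5 | 10 | 33% | 4.1 | 95% | 99% |
| 2-6 | 10 | 20 | 33% | 8.2 | 43% | about 58% |
| 2-6 | 10 | 10 | 67% | 5.8 | 71% | 99% |

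As an example, for 2-6 teeth with b = 10 and s = 10 the share is 100 × 2/(200 + 100) = 67%. For 2-4 teeth with b = 5 and s = 20 it is 16.7/(16.7 + 400) = 4%.

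**Validity.** With no true difference, the raw and adjusted tests both reject in about 5% of simulated trials, and the raw estimate shows no bias beyond simulation error (within 0.1 minute). Conditional on an observed imbalance the picture differs. A further simulation weighted towards fewer teeth, at 10-15 minutes per tooth and residual SD 10-15, took trials whose arm means differed by at least half a tooth. Among these the raw test rejected in 12% to 34% when there was no true difference. Fewer rejections in the better balanced trials offset this, which is why the overall rate stays near 5%.

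**CRC, if counted per patient as all teeth covered.** Section 4.1 gives only "percentage (%) of complete root coverage (CRC) at 12 months", without the unit. At an assumed 80% chance per tooth, independent teeth give 0.8² = 64% with 2 teeth and 0.8⁶ = 26% with 6. With a within-patient correlation of 0.4 (beta-binomial) these become 70% and 54%. For 2-6 teeth, the SD of the between-arm CRC difference that comes from tooth mix alone is 4.5 points if teeth are independent and 1.9 points at correlation 0.4. The total sampling SD of that difference is √(0.43 × 0.57 × 2/18) = 16.5 points in the first case and about 16.2 in the second. Tooth mix is thus (4.5/16.5)² = 7% or (1.9/16.2)² = 1.4% of the sampling variance, and is already part of it.

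**The case against.** The strongest objection is that patients are randomised individually with sealed opaque envelopes, so extent of surgery is not systematically tied to technique. This stands. A reader might infer that the comparison is confounded; the documents do not support that, and the simulation shows an unbiased estimate with correct type I error. What remains is true of any prognostic baseline factor left unadjusted in a trial of 36. Tooth count is distinguished only by its direct link to operating time and by costing almost nothing to use.

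Three further inferences also go too far:
- That nothing is analysed per tooth. Section 8.3 plans tooth-level analysis and a mixed model, and the recession and tissue measurements are made on teeth. The gap is confined to outcomes with one value per patient.
- That all these outcomes are to be compared as raw values. Only VAS pain has a named t-test. Duration and drug intake have no named test, and the CRC unit is unstated.
- That a patient may be treated in two separate fields. Section 7.2 describes one flap with one midline, and section 7.5 speaks of a single treated site.

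It is also fair to say that the size depends wholly on assumptions. With 2-4 teeth and 5 minutes per tooth the gain is small, and no size can be given for pain or drug intake. The objection limits the point to precision and chance imbalance but does not remove it.

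**Conclusion.** The point holds as a minor one, mainly for secondary outcomes. Extent of surgery has no upper limit, affects duration by construction, and is not used in allocation or in any planned between-arm comparison. The raw comparison remains valid. The cost is precision: tooth count explains about 4% to 67% of the variance in duration, and arm means differ by more than half a tooth in about 5% to 26% of trials. Both ranges rest on the assumed 2-4 or 2-6 equally likely teeth, 5-10 minutes per tooth and residual SD of 10-20 minutes. For pain and drug intake the dependence is plausible but not shown. For CRC the effect is small, and arises only if CRC is counted per patient as all teeth covered.

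One related silence deserves closing. The protocol does not say that the list of teeth to be treated is fixed before the envelope is opened. A reader might infer that the choice of teeth could follow allocation. Nothing in the documents says so, but if it did, the count would be a post-randomisation variable and unsafe as a covariate.

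**What to change.** 1. State in section 5.1 that the teeth to be treated are fixed and recorded on the CRF before the envelope is opened.
2. In section 8.3, name the between-arm analysis of duration, VAS pain and drug intake, with the recorded number of teeth as a covariate. Permuting within strata of that number is an alternative that fits the permutation p-values already planned.
3. State the unit of CRC. If it is analysed per patient as all teeth covered, keep Fisher's exact test as planned and add a sensitivity analysis adjusted for the number of teeth.
4. Minutes per tooth may be reported descriptively but should not replace the adjusted comparison. The timed interval starts at anaesthesia and so has a fixed part. If duration is a + b × k for k teeth, minutes per tooth is a/k + b, which still depends on k and makes small cases look slow.

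The cost is one CRF line, a few sentences in sections 5.1 and 8.3, and one degree of freedom in the adjusted comparisons. The count is available from the recession readings at screening, so no new measurement is needed.

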5. STUDY DESIGN

5.1. Description of the protocol

The present research is a monocentric prospective parallel randomized controlled clinical trial.

Patients presenting multiple gingival recessions in the maxillae will be enrolled in the study after having signed an informed consent. Recessions will be treated by means of two mucogingival surgery techniques: modified coronally advanced flap (MCAF) and modified coronally advanced tunnel technique (MCAT), in association with the use of a collagen matrix (CM).

An allocation sequence by means of a computer-generated random list will be created and a sealed opaque envelope will contain the type of treatment assigned to each patient. The opaque envelope will be opened immediately after performing anesthesia.

5.2. Duration of study

Each patients will be followed for 12 months after surgery.

6. SELECTION OF PATIENTS

The present study will be reported according to the CONSORT statement for improving the quality of reports of parallel-group randomized trials (<http://www.consort-statement.org/>). This will be a parallel monocentric prospective randomized controlled clinical trial.

Patients requiring root coverage procedures from the Department of Periodontology of San Raffaele Hospital will be enrolled in the study.

6.1. Inclusion criteria

Subjects must be males and females of at least 18 years of age with:

- multiple (i.e., at least 2) Miller Class I and/or II gingival recessions located in the maxillae, with an apico-coronal extension (i.e., defect depth > 1 mm with at least one defect > 2 mm) and with at least 1 mm of residual keratinized tissue,
- good general health, with no systemic diseases that could influence the outcome of the therapy,
- healthy periodontal conditions (i.e., no presence of sites ≥ 4 mm and/or presence of intra-bony defects in the selected sites),
- adequate oral hygiene (full mouth plaque score (FMPS) of <25% at baseline (following initial oral hygiene instructions and prophylaxis),
- an adequate control of inflammation (full mouth bleeding score [FMBS]) of <25% at baseline (following initial oral hygiene instructions and prophylaxis).

Subjects must have voluntarily signed the informed consent before any study related action and must be committed to the study and the required follow-up visits.

6.2. Exclusion criteria

- subjects who currently smoke >10 cigarettes/day,
- female subjects who are nursing, pregnant, or plan to become pregnant,
- contraindication against oral surgical interventions,
- contraindication against use of Fibro-Gide (acute infection in the area of surgery and patient with collagen allergy)

7. STUDY PROCEDURE

7.1. Pre-treatment procedures

Cause-related therapy will be completed on all patients prior to surgery. In particular, patients will receive oral hygiene instructions (roll technique) to eliminate the wrong habits related to the etiology of the recession at least 2 months before surgery.

7.2. Surgical procedures

Two experienced practitioners ([name] and [name]) will perform the surgical session according to the technique as presented by Zucchelli & [name] 2000 and Aroca et al. 2013.

- Modified coronally advanced flap (MCAF)

After local anesthesia, a horizontal incision is made to include one tooth on each side of the teeth to be treated. The horizontal incision of the envelope flap consists of oblique sub-marginal incisions in the interdental areas, incisions which continue with the intra-sulcular incision at the recession defects. Each surgical papilla (SP) is dislocated with respect to the anatomic papilla by the oblique sub-marginal interdental incisions; in particular, the surgical papilla mesial to the flap midline are dislocated more apically and distally, while the papilla distal to the mid-line are shifted in a more apical and mesial position.

The envelope flap is raised with a split-full-split approach in the coronal-apical direction: the surgical papilla is dissected in a split-thickness manner, while gingival tissue apical to the root exposures is raised in a full-thickness manner (to provide that portion of the flap critical for root coverage with more thickness). Finally, the most apical portion of the flap is elevated in a split-thickness manner to facilitate the coronal displacement of the flap.

The portion of the root exposure with loss of clinical attachment (gingival recession plus probeable gingival sulcus/pocket) are mechanically treated with the use of curettes and EDTA is applied for 2 minutes.

The remaining tissue of the anatomic interdental papilla is de-epithelialized to create connective tissue beds to which the surgical papilla are sutured.

A sharp dissection into the vestibular lining mucosa is then carried out to eliminate muscle tension. Flap mobilization is considered “adequate” when the marginal portion of the flap is able to passively reach a level coronal to the CEJ at each single tooth in the surgical site. The flap, in fact, should be stable in its final position even without the sutures.

The porcine-derived bio-resorbable collagen matrix (CM) (Fibro-Gide) is now prepared for placement on the interested areas: the width of the matrix must be reduced to 3-4 mm and the matrix has to adapt to the receiving tissues, when placed, a suture (6/00) must be used to hold it in position. Sling sutures (6/00) are performed to accomplish a precise adaptation of the buccal flap on the exposed root surfaces and to stabilize every single surgical papilla over the interdental connective tissue bed.

- Modified coronally advanced tunnel technique (MCAT)

Immediately before surgery, composite stops are placed at the contact points to prevent collapse of the future suspended sutures into the inter-proximal spaces.

After local anaesthesia, root planing of the exposed root surface is performed by means of hand instruments. Ethylenediaminetetraacetic (EDTA) is applied on the sites.

Subsequently, intra-sulcular incisions were placed and muco-periosteal flap separation are raised using sharp tunnel elevators. The muco-periosteal dissection is extended beyond the muco-gingival junction (MGJ) and under each papilla, to allow passive, tension-free mobilization in coronal direction. Muscle fibres and any remaining collagen bundles on the inner aspect of the flap alveolar mucosa are cut using Gracey curettes with extreme care in order to obtain a passive coronal positioning of the flap and the papilla and to avoid perforation of the flap.

The porcine-derived bio-resorbable collagen matrix (Fibro-Gide) is now prepared for placement on the interested areas: the width of the matrix must be reduced to 3-4 mm, then it can be inserted under the CAMT by starting at the deepest recession. Then, the site is rinsed with saline solution to remove any clot. The matrix has to be held in position using a suture (6/00).

Finally, the flap is positioned coronally to CEJ by means of suspended sutures (6/00) around the contact points.

At surgery, the duration of the full procedure will be evaluated (from anesthesia to suture).

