8. STATISTICAL CONSIDERATIONS

8.1. Sample size calculation

The range of mean root coverage percentage of the two mucogingival techniques which can be found in literature varies between 85% and 95%. While the value of variability (SD) obtained in previous articles is 10%. On the basis of these settings, the sample dimension has been calculated using $\alpha = 0.05$ and the power (1- β) of 80%. The minimal significant value considered is 10%.

So, the needed number of patients to be enrolled in this study is 17 for the test group MCAF + Fibro-Gide and 17 for the MCAT + Fibro-Gide. However, the number of patients will be increased of 1 patient for each arm considering the possibility of dropout, so the required number will be 18 for each group.

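### Two surgeons operate, but the plan describes no stratification by surgeon, no rule for who operates and no surgeon term in the analysis, so surgeon aligned with technique is not excluded

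*Combined protocol and SAP*

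**What the plan says.** Section 7.2 (Surgical procedures) gives the operations to "Two experienced practitioners" and describes two techniques, each from its own cited source. It does not say how patients are divided between the two, or whether each operates in both arms.

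Section 5.1 (Description of the protocol) gives the allocation method: "An allocation sequence by means of a computer-generated random list will be created", with one sealed opaque envelope per patient. On timing it says: "The opaque envelope will be opened immediately after performing anesthesia". It mentions no strata, blocks or surgeon factor, and does not say when the operating surgeon is chosen.

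Section 8.1 plans "17 for the test group MCAF + Fibro-Gide and 17 for the MCAT + Fibro-Gide", then adds one patient per arm for dropout, "so the required number will be 18 for each group".

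Section 8.3 plans t-tests, Fisher's exact test, permutation p-values and a mixed model with patient and tooth factors. Surgeon does not appear. The calibration in section 7.6 concerns the examiner's measurements, not the operators.

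**The concern.** In a trial of two surgical techniques, the operator is the most obvious rival explanation for a difference in root coverage. Randomisation protects against it only if the operator is settled independently of the arm. If the operator can be chosen once the arm is known, for example according to who is more at home with which technique, any difference between the surgeons enters the technique comparison. If each surgeon performed only one technique, no later adjustment could separate the two.

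Even with the surgeon settled beforehand, a list that ignores surgeon leaves the split to chance. An analysis that ignores surgeon then leaves the between-surgeon variation in the error term. Duration of surgery, a secondary outcome in section 4.2, would be exposed in the same way.

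**Working it through.** **Inputs from section 8.1.** Difference 10 points ("The minimal significant value considered is 10" percent), SD 10 points ("the value of variability (SD) obtained in previous articles is 10" percent), "the power (1- β) of 80" percent, alpha 0.05 (taken as two-sided), 18 enrolled per arm. **Assumptions, because the documents give no figure:** a gap between surgeons of 2.5, 5 or 10 points in mean root coverage; 18 patients per surgeon; arms of exactly 18:18; SD 10 within surgeon.

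**1. The plan's own sample size.** The normal formula gives n = 2(1.96 + 0.84)² × 10²/10² = 15.7, so 16 per arm. The t-test version gives 16.7, so 17 per arm with power 80.7%. The stated 17 reproduces.

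**2. Surgeon fully aligned with technique, no true technique difference.** The whole gap appears as a technique effect. The standard error is 10 × √(2/18) = 3.33, the noncentrality is gap/3.33, and there are 34 degrees of freedom.

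| Surgeon gap | Noncentrality | False significant result |
|---|---|---|
| 2.5 | 0.75 | 11% |
| 5 | 1.5 | 31% |
| 10 | 3.0 | 83% |

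**3. Surgeon fixed before the envelope is opened, list ignores surgeon.** Let X be the number of one surgeon's 18 patients who fall in one arm. X is hypergeometric (36, 18, 18), with mean 9 and SD 1.52.
- An 11:7 split or worse: P(|X − 9| ≥ 2) = 0.318, about 32%.
- A 12:6 split or worse: P(|X − 9| ≥ 3) = 0.094, about 9%.
- The shift in the technique estimate is gap × (2X − 18)/18. At 11:7 this is gap × 4/18, or 1.1 points for a 5-point gap and 2.2 for a 10-point gap. At 12:6 it is gap × 6/18, or 1.7 and 3.3 points.
- Over all allocations the mean shift is zero. Its SD is gap × 2 × 1.52/18 = gap × 0.169, or 0.8 points for a 5-point gap and 1.7 for a 10-point gap.

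**4. Operating characteristics in case 3, analysis without surgeon.** In a simulation of 20,000 trials, type I error is 4.8% at a 5-point gap and 5.0% at 10 points. Power for a 10-point technique effect is 81% and 74%. As a cross-check, ignoring surgeon inflates the SD to about √(100 + gap²/4), which is 10.3 and 11.2, and the t-test formula with these SDs gives the same powers.

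**5. Stratified 9:9 within surgeon, surgeon in the model.** The noncentrality is 3.0 on 33 degrees of freedom. Power is about 83% and type I error about 5%, whatever the gap.

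**6. Adjustment alone, without stratification.** The variance of the technique estimate grows by 1/(1 − r²), with r = (2X − 18)/18. At 11:7 this is 1.05 (standard error +2.6%, power 81%). At 12:6 it is 1.125 (standard error +6%, power 78%). Adjustment therefore recovers most of the loss under chance imbalance.

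**The case against.** The strongest reply is that the protocol is silent here and states nothing wrong. Several stronger readings are tempting, and the documents do not support them.

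- *That the list is unblocked or unstratified.* Section 5.1 does not say so. A fixed 18 per group suggests some restriction, since simple randomisation of 36 gives exactly 18:18 only 13% of the time. What can be said is that no restriction is described.
- *That each surgeon performs one technique.* This is only a permitted reading of 7.2. Both surgeons might perform both techniques, or operate together. Section 3 says the department's clinicians use these techniques routinely. An envelope opened after anaesthesia makes it plausible that the operator is already settled. The timing is not decisive, however: 7.2 places a preparatory step specific to the tunnel technique before anaesthesia, while 5.1 reveals the arm only afterwards, and these two passages need to be reconciled.
- *That adjustment is too weak at this size, so only a new randomisation scheme will do.* Step 6 shows otherwise for chance imbalance. Adjustment fails only under full alignment, and fixing the surgeon first prevents that.
- *That simple randomisation would leave the trial short.* The smaller arm would fall below 17 in 62% of such lists, but the total stays at 36. Power is 82.5% at 16:20 and 81.1% at 14:22, both above the 80.7% of 17:17. It falls below that figure only from 13:23 (79.9%).

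It also stands that a 10-point gap between two surgeons both called experienced is an upper-end assumption, and that every figure here is on mean root coverage. The primary outcome, complete root coverage, is not quantified. The missing operator rule and the missing surgeon term remain.

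**Conclusion.** The point holds as a gap in the plan, not as a demonstrated bias. Nothing in the protocol excludes surgeon being aligned with technique. Full alignment would raise the chance of a false significant result to about 11%, 31% or 83% at assumed gaps of 2.5, 5 or 10 points. If the surgeon is fixed before allocation, there is no systematic bias and type I error stays near 5%. The cost is then chance imbalance and a loss of power from about 83% to 81% at a 5-point gap or 74% at a 10-point gap, if surgeon is left out of the analysis.

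These figures rest on the assumed gaps, equal caseloads, 18:18 arms and the plan's SD of 10 on mean root coverage. Which of the two situations applies depends on a rule the protocol does not give. The remedy is a worthwhile, inexpensive improvement. It matters most before enrolment, because full alignment cannot be undone afterwards.

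**What to change.** - **Section 5.1:** state that the operating surgeon is assigned and recorded before the envelope is opened. Use one computer-generated 1:1 list per surgeon, in permuted blocks (preferably of varying size). Blocking alone, without separate lists, would not balance surgeons.
- **Section 7.2:** state that each surgeon performs both techniques.
- **Section 8.3:** include surgeon as a factor in the mixed model and as a stratum in the between-group tests, including the test of complete root coverage. Carry out the planned permutations within surgeon.

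The cost is a second set of envelopes and a few sentences of protocol text. Arm totals may differ from 18:18 by one or two if caseloads are uneven, and the surgeon has to be settled before allocation. The sample size does not change.

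### Read in the order written, the MCAT-only composite stops come before both the opening of the allocation envelope and the start of the surgery clock

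*Combined protocol and SAP*

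**What the plan says.** Four parts of the protocol bear on the order of events on the day of surgery.

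- **Section 7.2, MCAT.** The first step is "Immediately before surgery, composite stops are placed at the contact points". The next paragraph begins "After local anaesthesia, root planing of the exposed root surface is performed by means of hand instruments".
- **Section 7.2, MCAF.** The description begins "After local anesthesia, a horizontal incision is made to include one tooth on each side of the teeth to be treated". It mentions no composite stops.
- **Section 5.1.** Allocation comes from a computer-generated list held in sealed envelopes. "The opaque envelope will be opened immediately after performing anesthesia".
- **Section 4.2.** A named secondary outcome is "duration of surgery (from anesthesia to last suture"). Section 7.2 repeats the definition: "At surgery, the duration of the full procedure will be evaluated (from anesthesia to suture").

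The flow-chart (section 2) puts consent, eligibility and the baseline PPD, BoP, PI, REC, KTW and GT at screening, and randomization and surgery together on Day 0. The synopsis describes the trial as open label.

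**The concern.** The stops are described for one arm only. If they are placed before anaesthesia, someone must already know that the patient is in that arm, yet section 5.1 withholds the arm until anaesthesia has been given. Staff cannot follow both sections as they stand.

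Two things are at stake.

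- **Late opening of the envelope.** This is the protocol's timing safeguard in an open-label trial. If the arm is known earlier, a case can more easily be deferred, or a patient can withdraw, with the allocation in view. Section 8 defines no analysis population and no handling of patients lost after allocation, and the dropout allowance is one patient per arm (17 raised to 18), so even a single such case would use up an arm's margin.
- **Duration of surgery.** A step before anaesthesia is not timed. If only MCAT patients have that step, the comparison of durations is shifted in one direction, towards MCAT looking quicker.

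**Working it through.** **The plan's own figure.** The only computed figure is the sample size in section 8.1: difference 10 points, SD 10, alpha 0.05, power 80%. Sidedness is not stated; two-sided is assumed here.

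- Normal approximation: n = 2 × (1.960 + 0.842)² × (10/10)² = 15.7, so 16 per arm.
- Two-sample t-test: 16.71, so 17 per arm, with power 80.7% at 17.

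The stated 17 reproduces. It concerns root coverage and does not depend on this point.

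**Order of events.** The events to be ordered are stops, anaesthesia, envelope and last suture. Section 5.1 fixes anaesthesia, then envelope. Sections 4.2 and 7.2 fix the clock as running from anaesthesia to the last suture. Only the position of the stops is open.

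| Reading | Arm known before envelope? | Stops inside clock? |
|---|---|---|
| (a) Stops before anaesthesia, MCAT patients only (order as written) | Yes | No |
| (b) Stops before anaesthesia in every patient (not stated) | No | No, but omitted in both arms alike |
| (c) Stops after anaesthesia and envelope, with surgery taken to mean the incision (not stated) | No | Yes |

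Two features of the text favour (a). The stops are written ahead of the paragraph that begins after anaesthesia. The protocol's own duration of surgery starts at anaesthesia, so on that definition a step before surgery is a step before anaesthesia. Both are inferences from wording; neither excludes (c).

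**Effect on duration under (a).** Let t be the mean time to place the stops.

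- Recorded MCAT mean = MCAT mean with stops counted − t.
- Recorded difference (MCAT − MCAF) = difference with stops counted − t.

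The direction is fixed and the size is t. The documents give neither t nor an SD for duration. If t were between 5 and 15 minutes (an assumption), the difference would shift by 5 to 15 minutes in favour of MCAT.

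**Effect on allocation under (a).** By the flow-chart, consent, eligibility and baseline measurements precede Day 0. Early knowledge of the arm therefore cannot influence those steps. The route that remains is deferral or withdrawal at the surgical visit.

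**The case against.** The strongest reply is that section 7.2 describes operative technique taken from cited papers, in mixed tenses, and is not a trial timeline. Section 5.1 alone governs allocation. The stops are placed before surgery, not expressly before anaesthesia, so the sequence anaesthesia, envelope, stops, root planing respects section 5.1 and keeps the stops inside the clock. This stands as a possible reading, and it means the conflict is not proven in every reading. It does not remove the need for a clarification, because the order of steps and the clock definition point the other way and no text settles it.

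It is also fair to say that operative time without preparatory work is a legitimate, narrower quantity. But section 7.2 calls the timed interval the full procedure, and a step required in one arm only should be either counted or openly excluded.

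Three stronger conclusions are tempting and are not supported.

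- A reader might infer that allocation concealment fails for the trial as a whole. The documents show sealed opaque envelopes, with consent and baseline measurements done beforehand. Only late deferral or withdrawal remains.
- A reader might infer a quantified false-positive rate for duration. With 18 per arm and a two-sided t-test, assumed inputs give anything from 11% (5 minutes, SD 20) to 99% (15 minutes, SD 10), which is too wide to be informative. Section 8.3 does not list duration among the variables for the t-test, although its general reference to numerical data could cover it.
- A reader might infer that the plan has to accept one fault or the other. It does not: under (a) both occur together, and under (c) neither does.

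**Conclusion.** The point holds as an inconsistency between sections 5.1 and 7.2 that carries over to the duration outcome in section 4.2. In the order written, the arm is known before the envelope is opened, and MCAT duration is understated by the time taken to place the stops.

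This rests on two assumptions: that the order of steps in section 7.2 is meant literally, and that only MCAT patients receive stops. The text favours both but states neither outright.

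The direction of the bias in duration is certain under those assumptions; its size is unknown. The effect is confined to one secondary outcome and to a residual risk of deferral or withdrawal after the arm is known. The primary outcome (CRC at 12 months), the sample size and alpha are unaffected. It should be corrected, because placement times that were not recorded cannot be recovered after patients have been treated.

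**What to change.** Reconcile sections 4.2, 5.1 and 7.2 so that they state:

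1. whether the composite stops apply to one arm or to all patients;
2. that no arm-specific step precedes the opening of the envelope, with the envelope opened no earlier than section 5.1 now provides. Moving it ahead of anaesthesia would create the early disclosure that the rule is meant to prevent;
3. that the duration clock starts, in both arms, at one common event that precedes every arm-specific step and ends at the last suture, so that stop placement is counted. If the stops remain before the clock, their time should be recorded and added to the MCAT duration.

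How the surgical sequence is reconciled is for the sponsor to decide.

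The cost is a few sentences. If item 2 is met by placing the stops after the envelope, the present start at anaesthesia already satisfies item 3 and the definition of duration need not change. If the stops stay outside the clock, the cost is one extra recorded time.
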